### 4.2 Sensitivity and Secondary Analyses

Sensitivity analyses will be conducted to examine the robustness of the results, including handling missing data via multiple imputations. Additionally, an evaluation will be made to determine how deviations from the original inclusion criteria may have affected the results. Secondary exploratory analyses will investigate potential mediators and moderators of the intervention effect, such as baseline levels of binge eating, depressive symptoms, and diabetes-related distress, as well as individual characteristics (e.g., age and gender).

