# Better treatment of type 2 diabetes and Binge Eating Disorder: Statistical Analysis Plan

## 1. Background

**Primary Objective:** The purpose of this pilot study is to evaluate the effect of cognitive behavioral therapy (CBT) on the number of weekly binge eating episodes among individuals with binge eating disorder (BED) and type 2 diabetes. As this is a pilot RCT, the focus will be on estimating effect sizes and identifying trends rather than testing hypotheses. The aim is to gather information on the potential effect of the intervention, which can inform the design of a future full-scale RCT.

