### Secondary Outcomes:

- **HbA1c:** Glycemic control will be measured by changes in HbA1c levels, assessed through blood tests, where HbA1c represents the average blood glucose over the past 2-3 months. HbA1c will be measured via blood tests at Odense University Hospital (OUH).
- **Time in Range (TiR) and Time Above Range (TAR) / Time Below Range (TBR):** Glycemic control will also be assessed using continuous glucose monitoring (CGM), which measures how long the participant's blood glucose stays within the desired range (TiR), as well as the time spent above and below the target range (TAR and TBR). The CGM sensor is blinded and is worn by participants for one week before being returned to OUH.
- **BED-Q:** Binge eating symptoms and behaviors will be assessed using the BED-Q (Binge Eating Disorder Questionnaire), a self-report tool that evaluates both the frequency and intensity of binge eating episodes.
- **EDE-Q:** Eating disorder symptoms will be further assessed with the EDE-Q, one of the most widely used tools in binge eating research.
- **MDI:** Depressive symptoms will be assessed using the Major Depression Inventory (MDI), a self-report questionnaire that measures symptoms of depression based on clinically defined criteria.

- **PAID-20:** The Problem Areas in Diabetes-20 will be used to assess diabetes-related distress, where participants report feelings and difficulties related to their diabetes treatment and management.
- **Lipid Profile:** Blood tests will be used to measure the lipid profile, including levels of total cholesterol, triglycerides, and HDL cholesterol.
- **BMI:** Weight and BMI will be measured via self-report on the EDE-Q, as weight will not be measured directly in the study. This choice has been made because weight loss is not the goal of the intervention, and to avoid influencing participants' expectations.
- **Blood Pressure:** Systolic and diastolic blood pressure will be measured using an automatic blood pressure monitor, providing information on changes in cardiovascular risk. Blood pressure will be measured using the MAM function (Multi-Measurement Mode) in calm clinical settings at OUH.

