## 4. Statistical Analysis

### 4.1 Primary Analysis

Since this is a pilot study, the primary analyses will be exploratory and reported as descriptive statistics and inferential analyses. Changes in weekly binge eating episodes between groups will be estimated by:

- Mean and standard deviation for each group at both baseline and post-intervention
- Effect size calculated with Cohen's d to quantify the difference between groups
- 95% confidence intervals for the estimated effects
- Mixed-effects models: A mixed-effects model will be used to assess intraindividual changes in the number of binge episodes over time, accounting for both the intervention effect and individual differences. This model will allow time and group effects to be included as factors, and individual variation will also be considered. As this is a pilot study, the analysis will be exploratory and will not aim to test formal hypotheses with sufficient statistical power.
- Given the potential risk of reduced statistical power due to the limited sample size, alternative statistical methods, such as paired t-tests or Wilcoxon signed-rank tests, will be considered if necessary.

As there is insufficient power to draw definitive conclusions about the intervention's effect, the focus will be on identifying trends and possible effect sizes that can inform a future full-scale RCT.

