### 4.3 Handling of Missing Data

Missing data will be handled by multiple imputations under the assumption of missing at random (MAR). This will ensure that missing data do not introduce bias into the results. Imputation will be performed on the relevant variables, and both baseline and follow-up data will be included in the imputation model.

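### Do the unassigned mediator and moderator roles, with an imputation model that names no interaction, bias the moderator results towards zero?

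*SAP*

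**What the plan says.** SAP section 4.2 has two separate strands. One is sensitivity analysis, where multiple imputation appears as an example. The other is exploratory analysis of "potential mediators and moderators of the intervention effect, such as baseline levels of binge eating, depressive symptoms, and diabetes-related distress", with age and gender added as further examples. The list is illustrative, and no variable is labelled mediator or moderator. Two of the constructs are also secondary outcomes in section 3: depressive symptoms, through the MDI, and distress, where "The Problem Areas in Diabetes-20 will be used to assess diabetes-related distress".

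Section 4.3 makes multiple imputation under missing at random (MAR) the approach to missing data. On content it says: "Imputation will be performed on the relevant variables, and both baseline and follow-up data will be included in the imputation model". On the result it says: "This will ensure that missing data do not introduce bias into the results". Neither a group-by-moderator term nor imputation by arm is mentioned or ruled out.

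For the primary mixed model, section 4.1 says: "This model will allow time and group effects to be included as factors". The pilot is meant to gather information "which can inform the design of a future full-scale RCT" (section 1).

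**The concern.** A mediator has to be something treatment can change. Baseline binge eating, age and gender cannot be changed by it, so they can only be moderators. If the baseline qualifier also covers depression and distress, which is the natural reading, section 4.2 announces mediator analyses and names no possible mediator. If it covers only binge eating, two of the five named variables could be either.

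The role matters for imputation. A moderator analysis is compatible with the imputation model only if that model lets the treatment effect vary with the moderator. A main-effects model gives every imputed participant the same CBT effect whatever the covariate value, so imputed outcomes dilute a real interaction. Confidence intervals show imprecision but not dilution. A true moderator could then look weaker than it is to those designing the full-scale trial, while section 4.3 tells the reader that bias has been dealt with.

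**Working it through.** The SAP gives no sample size, missing rate, standard deviation or effect size, so there is no stated figure to reproduce. All inputs below are assumptions chosen to test the mechanism.

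**Closed form.** Let b3 be the true interaction, p1 and p0 the shares of outcomes missing completely at random in the CBT and waitlist arms, and w1 = (1−p1)/[(1−p1)+(1−p0)] the CBT share of observed outcomes. A main-effects imputation model gives both arms the pooled slope, which exceeds the waitlist slope by w1·b3.

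- CBT slope, relative to the true waitlist slope, after imputation: (1−p1)·b3 + p1·w1·b3
- Waitlist slope, on the same scale: p0·w1·b3
- Share of b3 kept: 1 − p1(1−w1) − p0·w1

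With equal missingness w1 = 1/2 and the share kept is 1−p: 0.90, 0.80 and 0.70 at 10%, 20% and 30%. With 30% and 10% missing, w1 = 0.7/1.6 = 0.4375 and the share is 1 − 0.3×0.5625 − 0.1×0.4375 = 0.7875.

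This formula needs missingness unrelated to the moderator within arm. With missingness depending on the moderator (assumed logistic slope of 1, 2,000 per arm, 30% missing) the share kept is 0.61, so 1−p is not a general result under MAR.

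**Simulation of the share kept.** Y = −0.5·group + 0.5·M + b3·group·M + 0.8·noise, with b3 = −0.5, 10 imputations and 6,000 trials per cell, outcomes missing completely at random:

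| Per arm | 10% | 20% | 30% |
|---|---|---|---|
| 20, no interaction in imputation | 0.880 | 0.779 | 0.659 |
| 60, no interaction in imputation | 0.897 | 0.790 | 0.683 |

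With the interaction in the imputation model the share was 0.992 to 1.017 in all cells. A second set-up (true interaction 0.50, residual SD 1, totals of 40, 60 and 400) agreed: 0.44–0.45, 0.38–0.40 and 0.33–0.35 without the term, and 0.49–0.50 with it. Analysis of **observed data only** gave about 0.50, so there was no attenuation.

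**Error as well as bias.** Root mean squared error (RMSE) of the interaction estimate, first model, 2,000 trials:

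| Per arm, missing | Without term | With term |
|---|---|---|
| 20, 20% | 0.281 | 0.319 |
| 20, 30% | 0.294 | 0.365 |
| 60, 20% | 0.173 | 0.172 |
| 60, 30% | 0.200 | 0.181 |

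In the first row the bias is 0.114. Squared bias is 0.114² = 0.013. Variance without the term is 0.281² − 0.013 = 0.066, against 0.319² = 0.102 with it. Omission adds 0.013 in squared bias and saves 0.036 in variance. The balance reverses as the sample and missing rate grow, and a larger true interaction would also tip it, because the bias scales with b3.

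**Against the text.** Three conditions must all hold before any attenuation occurs:

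1. Data relevant to the moderator model are missing.
2. That model is fitted to imputed data.
3. The imputation model omits the interaction.

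The SAP settles none of them. Section 4.2 mentions imputation under sensitivity analysis, in a different sentence from the moderator work, whereas section 4.3 reads as a general rule, so condition 2 is open. For condition 3, the reference to relevant variables can include interactions. The time and group terms in section 4.1 describe the primary mixed model and do not define the imputation model.

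**The case for a change.** The strongest case for a change is that the SAP has its own sections on moderators and imputation, so this is not detail left to a protocol. The no-bias sentence is also unconditional: MAR alone does not secure it, because the imputation model must be compatible with the analysis model as well. Under the simulated mechanism, imputing without the interaction brings in a bias that simply using observed data would avoid. In a pilot whose purpose is effect estimates, attenuation is harder to see than imprecision. Correcting the text would need only a few lines.

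Part of this stands. The sentence in section 4.3 is too strong as written, and section 4.2 should not be read as defining any mediator analysis. The lower RMSE at 20 per arm is not an argument for omitting the term either, since it depends on the assumed interaction size.

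What does not stand is the step from silence to bias. The attenuation belongs to an imputation model that the SAP never specifies. An analyst who fits a group-by-moderator model and imputes for it would ordinarily carry that term, or impute by arm, or use observed data for exploratory work of this kind. Fixing the interaction in advance would also cost precision in a small sample, which makes it a trade-off and not a plain correction. The aim in section 1 concerns the effect of the intervention and does not mention moderators.

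**Conclusion.** No change to the plan follows. The mechanism is correct: under main-effects imputation with outcomes missing completely at random within arm, about 88%, 78% and 66% of a moderator effect is kept at 10%, 20% and 30% missing with 20 per arm, all assumed values. But the SAP does not prescribe that model, and both alternatives open to the analyst (including the term, or using observed data) gave essentially unbiased estimates in the simulations. At 20 per arm the bias at 20% missing (0.114) is well below the sampling SD with the term included (0.319).

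The textual residue is an illustrative list without roles, on whose natural reading every named variable is a baseline moderator, and a sentence that overstates what imputation secures. Both concern secondary exploratory analyses in a pilot that already disclaims adequate power, and the primary comparison is not affected. This is a gap that a competent analyst fills when writing the moderator models.

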### 4.3 Handling of Missing Data

Missing data will be handled by multiple imputations under the assumption of missing at random (MAR). This will ensure that missing data do not introduce bias into the results. Imputation will be performed on the relevant variables, and both baseline and follow-up data will be included in the imputation model.
